- On-board and train study site personnel
- Define study site opportunity/channels for study participant recruitment
- Create study site materials from approved IRB submission

Measure – Month 5-11 Participant Recruitment/Enrollment (Study Intervention)

- Total participants (205 minimum)
- Recruit potential participants by inclusion/exclusion criteria
- Participant downloads the Namida Lab, Inc. mobile app if they have access to a device
- Obtain informed consent from the study participant
- Obtain participant's history/demographics from surveys/questionnaires
- Sample Collection – Site-specific: Sample may be collected as a walk-in or scheduled appointment

Analyze – Month 5-11 Baseline Assessments/Study Intervention

- Study participant tear sample sent to Namida Lab, Inc.
- Namida Lab, Inc. conducts Melody® assay on participant samples
- Namida Lab, Inc. returns Melody® assay results to the study site investigator/clinician/personnel
- Study site clinician and Namida Lab, Inc. review Melody® assay results, if requested
- Study site clinician and study participant review Melody® assay results

Improve – Month 5-11 Follow-Up (Assessments of Study Endpoints/Safety)

- Study participant completes exit survey/questionnaire
- Study site personnel completes exit survey/questionnaire
- Namida Lab, Inc. distributes compensation to study participants
- Ongoing data analysis at Namida Lab, Inc.

Control – Month 12 End of Study Assessment

- Namida Lab, Inc. completes all data analysis from study site personnel and participants
- Namida Lab, Inc. closes sites/study

**Appendix A: Visual Diagram of Study Schematic*

1. Key Roles

[figure not shown]
[name].
VP of Product Development & Innovation
Principal Investigator
Namida Lab, Inc.
[name]
[name]
[contact]
[contact]

[name], MBA
Clinical Research Coordinator
Namida Lab, Inc.
[name]
[name]
[contact]
[contact]

2. Introduction: Background Information and Scientific Rationale

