5.3 Strategies for Recruitment and Retention

Target sample size:

- An a priori power analysis was conducted using G*Power v3.1.9.2 to determine the minimum sample size required to find significance with a desired level of power set at 0.80 and alpha (α) level at 0.05. Based on this analysis, it was determined that a **minimum of 205 participants** were required to ensure adequate power for a Pearson's Chi-square Test of Independence. (12, 13, 14)

The anticipated site participants' accrual rate will vary; all sites and participants will be located within the United States. Participants will be recruited from outpatient clinics, larger employers, and/or the general public. Participant recruitment venues are site-specific, for example, outpatient clinic monthly clinical breast exam events. Potential participants will be identified and approached using inclusion/exclusion criteria and site-specific events and/or communication channels.

While exact recruitment methods will be specific to each site, the material will be made available in versions suitable for flyers, email, post through social media, or distributed by mail. Forward-facing participant recruitment materials have been submitted separately with indications on how it can be personalization to each site.

The VIOLA Study participants are all women due to the development and validation of Melody®. The objectives and endpoints encourage minorities, employee volunteers, economically disadvantaged, and/or a medically underserved population to participate in the VIOLA Study. The justification for involving vulnerable populations is because they are primarily affected by disparities in the healthcare system. Employee volunteers are included because study sites provide current medical care and have a trusted relationship with the employee volunteer as a current patient.

Careful considerations have been included in the study design and recruitment process to ensure minimal harm/risks and maximum participant protection. Participants will have access to translated study materials and access to additional healthcare navigation if needed. Employers will not be notified of study participation or Melody® results; participation or nonparticipation is confidential. Each participant will receive a \$25 Walmart gift card when completing the VIOLA Study, and there is no cost to participate.

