10.1 Statistical and Analytical Plans

An a priori power analysis was conducted using G*Power v3.1.9.2 to determine the minimum sample size required to find significance with a desired level of power set at 0.80 and alpha (a) level at 0.05. Based on this analysis, it was determined that a minimum of 205 participants were required to ensure adequate power for a Pearson's Chi-square Test of Independence. (12, 13, 14) (Appendix L)

Each participant will be required to take an enrollment survey that collects information on race, ethnicity, and socio-economic status. Participant's addresses will be obtained as part of the requisition process for the CLIA lab, from which information on geographic location can be obtained. In addition to the factors listed above, the enrollment survey also collects information on status and type of health insurance, reproductive health, breast health knowledge, prior screening history, and family and personal history of cancer.

The exit survey has been designed to collect information on the participant experience with Melody® and comprehension of the information Melody® relayed through their site clinician. In addition, information is collected on participant's intention to schedule/participate in future screening mammograms and/or change in intention to participate in a previously scheduled screening mammogram.

Data will be analyzed using SPSS Statistics software. To determine the presence of significant changes, Unpaired T-tests or Mann-Whitney U-test will be used with a significance level set at P < 0.05.

Due to the effect of COVID-19 on screening rates, screening mammogram participation rates will be compared to rates reported for the state of Arkansas in 2019.

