The results of the power analysis can be found in Table 1 below. Remember that power analysis calculations using lower effect sizes will tell you that you need larger samples, but these are the calculations easiest to justify. The calculations in the H1 hypothesis (percentage difference in compliance between treated and untreated groups) are the initial power calculation. The second calculation under accounting for 10% drop-out, increases the sample size to account for the drop-out rate you requested. Based on the moderate effect size of $\Delta\% = 20\%$ with a power level of .80, we recommend you recruit 205 participants for this study split evenly between treatment and non-treated groups ($N = 103$ each).

Table 1
Minimum Sample Size Needed for Range of Effect Sizes for Each Study Hypothesis

Hypothesis	Power level	Effect Size			
		Effect	Low	Moderate	
H1: Compliance for Treatment vs Untreated groups	$\Delta\%$		10	20	30
Pearson's Chi-square test of Independence	.80	776	186	78	
	.85	886	214	88	
	.90	1038	248	104	
Accounting for 10% drop-out rate	$\Delta\%$		10	20	30
	.80	854	205	86	
	.85	975	235	97	
	.90	1142	273	114	
Minimum sample size	$\Delta\%$		10	20	30
	.80	854	205	86	
	.85	975	235	97	
	.90	1142	273	114	

Note. Alpha level = .05. The numbers represented here are the total number of participants that would be needed for the sample.

Write-up to include in a methods section (if needed)

An a priori power analysis was conducted using G*Power v3.1.9.2 to determine the minimum sample size required to find significance with a desired level of power set at .80, an alpha (α) level at .05. Based on this analysis, it was determined that a minimum of 205 participants (two groups of 103) were required to ensure adequate power for a Pearson's Chi-square Test of Independence. (Cohen, 1988; Erdfelder, Faul, & Buchner, 1996; Faul, Erdfelder, Lang, & Buchner, 2007).

References

Cohen, J. (1988). Statistical power analysis for the behavioral sciences (2nd ed.). Hillsdale, NJ: Lawrence Erlbaum Associates.

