
G*Power Screen-shots

Screenshots

Moderate Effect Size ($\Delta\% = 20$)

Power = .80

Test family	Statistical test		
z tests	Proportions: Difference between two independent proportions		
Type of power analysis			
A priori: Compute required sample size - given α, power, and effect size			
Input Parameters		Output Parameters	
Tail(s)	Two	Critical z	1.9599640
Proportion p2	.70	Sample size group 1	93
Proportion p1	0.5	Sample size group 2	93
α err prob	0.05	Total sample size	186
Power (1- β err prob)	.80	Actual power	0.8000056
Allocation ratio N2/N1	1		

Power = .85

Test family	Statistical test		
z tests	Proportions: Difference between two independent proportions		
Type of power analysis			
A priori: Compute required sample size - given α, power, and effect size			
Input Parameters		Output Parameters	
Tail(s)	Two	Critical z	1.9599640
Proportion p2	.70	Sample size group 1	107
Proportion p1	0.5	Sample size group 2	107
α err prob	0.05	Total sample size	214
Power (1- β err prob)	.85	Actual power	0.8527234
Allocation ratio N2/N1	1		

Power = .90

Test family	Statistical test		
z tests	Proportions: Difference between two independent proportions		
Type of power analysis			
A priori: Compute required sample size - given α, power, and effect size			
Input Parameters		Output Parameters	
Tail(s)	Two	Critical z	1.9599640
Proportion p2	.70	Sample size group 1	124
Proportion p1	0.5	Sample size group 2	124
α err prob	0.05	Total sample size	248
Power (1- β err prob)	.90	Actual power	0.9000032
Allocation ratio N2/N1	1		

N. Namida Lab, Inc. Policies for PHI Use and Disclosures (HIPAA)

POLICIES AND PROCEDURES FOR PHI USE AND DISCLOSURES

INTRODUCTION

These policies and procedures address handling, safeguarding, using, and disclosing protected health information (PHI). Under HIPAA, covered entities must ensure the privacy of a patients' protected health information.

PHI refers to all information (oral, paper-based documents, and electronic documents) that relates to an individual including but not limited to:

- Medical information
- Billing information
- Financial information
- Names and other identifying information such as:
 - Telephone numbers
 - Fax numbers
 - Electronic Mail addresses

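### The 0.80 power quoted for 205 participants was computed for 205 women split 1:1 into treated and untreated groups, but VIOLA exposes all of them and compares them with 2019 rates

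*Protocol*

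**What the plan says.** Protocol 5.3 and 10.1 both set power at 0.80 and alpha at 0.05. Section 10.1 concludes that a "minimum of 205 participants were required to ensure adequate power for a Pearson's Chi-square Test of Independence" and refers to Appendix L. Neither section mentions two groups.

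Appendix L does. It describes the hypothesis it sizes as the "percentage difference in compliance between treated and untreated groups", and its G*Power screenshots use "Proportions: Difference between two independent proportions" with an allocation ratio of 1. It then says "we recommend you recruit 205 participants for this study split evenly between treatment and non-treated groups", with 103 in each, and its suggested methods text reads "a minimum of 205 participants (two groups of 103) were required to ensure adequate power". The note to its Table 1 says: "The numbers represented here are the total number of participants that would be needed for the sample".

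The design is described differently elsewhere:

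- Section 4.1: every participant receives Melody, and there are no varying levels of exposure.
- Section 7.3.6: the schedule of events shows a single path.
- Sections 10.1, 10.2 and 10.4.2: the primary comparison is with 2019 participation rates, which 10.1 takes from the state of Arkansas.
- Sections 10.3 and 10.4.3: the secondary comparison sets each site's rate after the study against that site's own 2019 rate.

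The protocol gives neither a 2019 rate nor a 2019 denominator. The 0.50 in Appendix L is only a software input.

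**The concern.** Power belongs to a specific comparison. Here it was calculated for two concurrent groups drawn from the 205 recruits, about half of them untreated. In the study as planned, all 205 are exposed and the reference comes from outside the cohort. The precision of the comparison therefore depends on the 2019 rate, on its denominator and on how many participants have a known screening outcome. None of these enters the sizing as such.

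A reader of 5.3 or 10.1 who follows the reference to Appendix L will take 20 points at 0.80 power as the study's sensitivity. The same sentence also appears to cover the hypotheses that 10.2 examines by characteristic and by site, for which no calculation was made.

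**Working it through.** **1. The plan's own figure.** Inputs from Appendix L: p1 = 0.50, p2 = 0.70, two-sided alpha 0.05 (z = 1.96), allocation 1:1, 10% drop-out. For two proportions with pooled variance under the null:

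power = Φ{[d − 1.96·SE0] / SE1}, with SE0 = √[p̄(1−p̄)(1/n+1/m)] and SE1 = √[p_V(1−p_V)/n + p_2019(1−p_2019)/m].

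With n = m = 93: p̄ = 0.60, SE0 = 0.0718, SE1 = 0.0703, and (0.20 − 0.1408)/0.0703 = 0.842, so power = 0.800. Appendix L gives 0.8000056. The total is 2 × 93 = 186, and 186 × 1.10 = 204.6, rounded up to 205. The figures reproduce, as a 1:1 two-group calculation.

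**2. The planned overall comparison.** All recruits are exposed: 205 × 0.9 = 184.5, about 185 evaluable. The 2019 rate of 50% is an assumption (Appendix L's p1), and the 2019 denominator m is unknown, so it is varied. Power for 0.50 v 0.70, two-sided 0.05:

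| 2019 denominator m | Power |
|---|---|
| 60 | 0.800 |
| 185 | 0.978 |
| 500 | 0.998 |
| 1000 | 0.9995 |
| rate treated as fixed | above 0.999 |

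For m = 60: p̄ = (185×0.70 + 60×0.50)/245 = 0.651, SE0 = 0.0708, SE1 = 0.0728, and (0.20 − 0.1388)/0.0728 = 0.841. The stated 0.80 at 20 points is met only near m = 60.

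**3. Rise detectable with 80% power.** For a fixed rate, solve d = 1.96·√(0.25/n) + 0.8416·√[(0.5+d)(0.5−d)/n]. With n = 185: 0.0720 + 0.0303 = 0.102, or 10.2 points. The formula in step 1, set to 0.80, gives 11.1, 12.0 and 14.4 points for m = 1000, 500 and 185.

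Assumed 2019 rates from 30% to 70% give:

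- fixed rate: 9.1 to 10.2 points
- m = 1000: 9.8 to 11.1 points
- m = 500: 10.5 to 12.0 points
- m = 185: 12.4 to 14.5 points

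**4. Fewer known outcomes or clustering.** With 103 known outcomes against a fixed 50%: 0.0966 + 0.0399 = 0.136, about 14 points. With an illustrative design effect of 2, 185/2 = 92.5 effective women give 14.4 points.

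The break-even denominator also moves. With n = 103 and m = 60: p̄ = 0.626, SE0 = 0.0786, SE1 = 0.0788, and (0.20 − 0.1540)/0.0788 = 0.584, so power is 0.72.

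**5. A small group.** As an illustration, 20 women against a fixed 50%, for 20 points: (0.20 − 1.96×0.1118)/0.1025 = −0.187, so power is 0.43 (exact binomial 0.42).

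**The case against.** The best defence is that 2019 is the untreated group, so the two-proportion calculation still applies. The text of Appendix L does not allow this. Its Table 1 counts total participants in the sample, and it divides the 205 recruits themselves between both groups. Even on that reading, 205 exposed women against 2019 is not 93 against 93.

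A second defence is that 5.3 and 10.1 claim only a minimum for adequate power and do not repeat the split, which stands in an appended report. That is true. On the assumptions above, 205 is indeed adequate for 20 points overall unless the 2019 denominator is small. This limits the weight of the point, but Appendix L is the only source for the figure.

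Two cautions also stand. First, the figure cannot be called conservative without conditions. The 185 rests on the 10% drop-out alone, whereas the participant exit survey asks about the intention to schedule or complete a mammogram and makes later contact optional, and the provider survey counts mammograms scheduled. Second, the sites' own 2019 rates are a different comparator from the Arkansas rates, and some women may appear in both periods, so these independent-sample figures need not carry over to the secondary analysis.

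A reader might infer that Appendix L is miscalculated, that 205 is too few, or that an untreated group must be added. The documents support none of these: the arithmetic reproduces, and the protocol deliberately plans a single exposed cohort.

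**Conclusion.** The point holds as a mismatch between design and sizing. The 0.80 power and the 20-point difference belong to a treated-versus-untreated comparison that VIOLA does not make.

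For an overall VIOLA-versus-2019 rate, assuming 50% in 2019, independent women and two-sided 0.05, the figure is conservative if about 185 women have a known screening outcome and the 2019 denominator exceeds about 60. With fewer known outcomes the denominator must be larger. On the same assumptions, the rise detectable with 80% power is about 10 points against a fixed rate and 11 to 14 points against a rate estimated from 1000 down to 185 women. It is larger if outcomes are missing or women cluster within sites.

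The figure gives no assurance for the comparisons by characteristic or by site. It should be corrected, but it does not threaten the enrolment target.

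**What to change.** Keep 205.

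1. In Appendix L, delete the clause that splits the 205 recruits evenly into groups of 103, and the parenthesis on two groups of 103 in the suggested methods text. State that Table 1 and the screenshots show a two-group calculation that is not the VIOLA design.

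2. In 5.3, 10.1 and the Appendix L methods text, replace the power statement with one for a single exposed cohort, for example:

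> All participants receive Melody; there is no untreated group. With about 185 evaluable women (205 less 10%), two-sided alpha 0.05, an ASSUMED 2019 participation rate of 50% and independent observations, 80% power corresponds to a rise of about 10 percentage points if the 2019 rate is treated as fixed, or about 11 to 14 points if it is estimated from 1000 down to 185 women. The rise is larger if fewer outcomes are known (about 14 points with 103 women against a fixed rate) or if women cluster within sites. This covers only an overall VIOLA-versus-2019 rate, not comparisons by characteristic or site. It will be updated when the 2019 rate and denominator are stated.

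The cost is text in three places and no change to enrolment or data collection. The sponsor must supply the 2019 rate and its denominator. The choice between a chi-square test and the t-test or Mann-Whitney test, and the layout of the 10.4.2 table, are separate points that this change does not settle.

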30. COMPLETE AGREEMENT; SEVERABILITY

This Agreement supersedes all proposals, oral or written, all negotiations, conversations, discussions, agreements, and all past course of dealing between you and Namida Lab relating to the Software or the terms of its license to you, and may only be modified in writing signed by you and Namida Lab. In the event any term of this Agreement is held by a court of competent jurisdiction not to be enforceable, such unenforceability shall not affect the remaining terms of this Agreement in such jurisdiction or render unenforceable or invalidate such terms and provisions of this Agreement in other jurisdictions. Upon such determination that any of the terms or provisions of this Agreement are held to be invalid under any applicable statute or rule of law, they shall be severed from this Agreement and the remaining provisions of this Agreement shall be interpreted so as best to reasonably effect the intent of the parties and the parties agree to replace any invalid or unenforceable provisions in a mutually acceptable manner in order that the transactions contemplated hereby be consummated as originally contemplated to the greatest extent possible. No waiver of any right or obligation contained herein shall be given except in writing signed by the party against whom the waiver is sought to be enforced.

If you have any questions about this license agreement, please contact [contact].

[figure not shown]
You can also reach us by mail:

Namida Lab, Inc.
ATTN: Legal
[name]
[name], USA

[figure not shown]
*** YOU ACKNOWLEDGE THAT YOU HAVE READ THIS AGREEMENT, UNDERSTAND IT, AND AGREE TO BE
BOUND BY ITS TERMS AND CONDITIONS. ***

R. Namida Lab, Inc. Mobile App Participant Facing Screenshot(s)

[figure not shown]
Sign-up

[figure not shown]
Discovery

[figure not shown]
Eligibility

[figure not shown]
eConsent

Task list

Activities

Reminders

Feedback
